12.3. Interim analysis and early termination of study

12.3.1. Purpose and timing of the interim analysis

One interim analysis is planned to evaluate whether the study is achieving its principal objectives. The purpose of this interim analysis will be to decide on the suitability of continuing to enroll patients in the study. If it is determined that the principal objectives of the study have been achieved, then the study will be terminated and its results reported at conferences and published in relevant journals as quickly as possible.

The interim analysis will be started after the first year of the study has been completed, using the initial monitoring data accumulated since the start of the study. In the event that 200 patients have not yet been enrolled in the study at 1 year after initiation of the study, the interim analysis will be done when data for 200 patients become available. Finally, as a rule, patient enrollment will continue while the interim analysis is being conducted.

12.3.2. Method of interim analysis

The interim analysis will be carried out by the staff of the RAISE Study Statistical Center. To keep overall α error of the RAISE study below 5%, the Lan-DeMets α -spending function³⁶⁾ with the O'Brien-Fleming monitoring boundaries was used to adjust for multiple comparisons. Differences in values between the 2 study groups will be analyzed to determine if they are statistically significant or not. If the interim analysis reveals a lower rate of CAA during study period in the group receiving IVIG plus PSL as compared with the group receiving standard IVIG and Fisher's exact test yields a p value <0.0034, this will be considered sufficient statistical evidence to accept the study's main hypothesis and, barring other important considerations, the study will, in principle, be terminated.

12.3.3. Reporting and evaluating the interim analysis results

The report of the interim analysis will be submitted to the Efficacy and Safety Review Board, which will decide whether the study should be terminated or not. Based on the results of the interim analysis, the Efficacy and Safety Review Board will discuss the continuation of the study at the Steering Committee and inform the RAISE Study Principal Investigator of the decisions they have reached with respect to continuation of the study and publication of its results. If, based on careful review of the interim-analysis report, the Efficacy and Safety Review Board decides that all or part of the study should be terminated or its protocol changed, the RAISE Study Principal Investigator will carefully consider this recommendation and issue a final decision as to whether to terminate the study or change part of its protocol. If the study is to be terminated or continued with an amended protocol, the RAISE Study Principal Investigator will submit the corresponding documents to the Efficacy and Safety Review Board: either the Request for Permission to Terminate the Study or Request for

Protocol Amendment, respectively. Once permission is granted by the Efficacy and Safety Review Board, the study may be terminated or its protocol amended.

12.4. Analysis of secondary endpoints

Analysis of the secondary endpoints will also be carried out to provide additional data for consideration of the results of the principal analysis of the study. Correction for the multiplicity of tests will not be performed because of the exploratory nature of the secondary endpoints. Comparisons between groups will be performed as necessary, but it is important to note that, although no statistically significant differences can be reported, this should not be interpreted to mean that there are no real differences between the treatment groups.

12.4.1. Analysis of the secondary endpoint related to safety

Of the several secondary endpoints studied, the endpoint related to safety is based on the incidence of adverse events, and this endpoint will therefore require regular monitoring.

12.4.2. Analysis of secondary endpoints related to efficacy

The secondary endpoints related to treatment efficacy include incidence of CAA at week 4 after enrollment, Z scores for the right coronary artery and left main coronary trunk and anterior descending artery, days of fever after enrollment, incidence of need for additional rescue therapy, and serum levels of CRP at Weeks 1 and 2 after enrollment. These secondary endpoints will only be analyzed during the interim analysis and at the end of the study, and only as secondary endpoints; there will be no correction for the multiplicity of tests when these endpoints are analyzed.

It is expected that the incidence of CAA at week 4 after enrollment will be lower in the IVIG plus PSL group than in the IVIG group, as this result is expected to be correlated with the largest diameter attained during the enlargement of the coronary artery, while these treatments are being administered.

As for incidence of need for additional rescue therapy, this can be considered to reflect the effectiveness of the treatments. It is therefore expected that this incidence will be lower in the IVIG plus PSL group than in the IVIG group.

As for days of fever after enrollment and serum levels of CRP at Weeks 1 and 2 after enrollment, these can be considered endpoints that depend on the suppression of KD vasculitis achieved by the treatments. It is therefore expected that, as compared with standard IVIG treatment, the period required for days of fever after enrollment will be shorter, and that serum levels of CRP at Weeks 1 and 2 after enrollment will be lower, in the IVIG plus PSL group.

Fisher's exact test will be used to evaluate the incidence of CAA at Week 4 after enrollment

and the incidence of need for additional rescue therapy; the interval estimation will be done with exact confidence intervals based on the binomial distribution.

Z scores for the right coronary artery and left main coronary trunk and anterior descending artery, days of fever after enrollment, and serum levels of CRP at Weeks 1 and 2 after enrollment will first be tested for normality with the Kolmogorov-Smirnov test. Variables that are found to have a normal distribution will be compared using the unpaired t-test; those with a non-normal distribution will be compared using the Mann-Whitney U-test.

12.5. Termination of the study if the incidence of giant coronary aneurisms in the trial treatment group is high

In general, the most important goal in treating KD patients is to prevent giant coronary aneurysms, which require lasting medical treatment. Thus, if the incidence of giant coronary aneurysms is higher for patients receiving the trial treatment than for those receiving the standard treatment, the trial treatment will be considered ineffective in reducing the incidence of such aneurysms and the study will be promptly terminated.

In the most recent national survey in Japan, the incidence of giant coronary aneurysms was 0.35%. If we assume that these patients would be stratified as high-risk patients, the incidence of giant coronary aneurysm among patients in this study could ultimately be as high as 1.1%. Therefore, if 4 patients in the trial treatment group develop giant coronary aneurysms, the Data Coordinating Center will immediately report this fact to both the RAISE Study Principal Investigator and the Efficacy and Safety Review Board, and the Board will then carefully review the cases and decide whether the study should be terminated.

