12.2. Target number of subjects/ registration period/ follow-up periods

As mentioned in the background of the study (section 2.3.3., "Clinical hypotheses and reason for number of registrants"), the rate of CAA in the IVIG group is expected to be the same as in previous studies of this treatment, ie, approximately 18%. The study design has been established to determine whether the trial treatment (IVIG plus PSL) can achieve at least an additional 10% absolute reduction in the incidence of CAA during the study period, i.e. reduce the incidence rate to 8% or less. If the study requires a 3-year registration period and a 1-month follow-up period, and α is equal to 5% (2-sided) with a statistical power of 80%, the number of cases required for each group will be 176, for a total of 352 in the 2 groups. If a 10% drop-out rate is assumed, the final enrollment numbers are as follows.

Target number of subjects: 196 per group, for a total of 392 patients.

Registration period: 3 years. Follow-up period: 1 month after enrollment.

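### Section 12.5 gives two conflicting study-stopping provisions for giant coronary aneurysms and does not say which one governs

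*Protocol*

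**What the plan says.** Section 12.5 of the protocol has two paragraphs on stopping the whole study for giant aneurysms.

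The first is comparative and mandatory: "if the incidence of giant coronary aneurysms is higher for patients receiving the trial treatment than for those receiving the standard treatment", then IVIG plus PSL is deemed ineffective against such aneurysms and "the study will be promptly terminated". It gives no size of excess, no minimum number of cases, no test and no time at which the arms are compared.

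The second begins with a background rate. In the latest national survey "the incidence of giant coronary aneurysms was 0.35" per cent, and on the assumption that these patients would all be classed as high risk, "the incidence of giant coronary aneurysm among patients in this study could ultimately be as high as 1.1" per cent. It then sets a count in one arm: "if 4 patients in the trial treatment group develop giant coronary aneurysms, the Data Coordinating Center will immediately report this fact". The recipients of that report are the Efficacy and Safety Review Board and the Principal Investigator. What happens next is left to discretion: "the Board will then carefully review the cases and decide whether the study should be terminated".

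No sentence there or elsewhere in section 12 ranks the two paragraphs.

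**The concern.** The two provisions differ in trigger (any excess over the control arm, against four trial-arm cases whatever the control count) and in consequence (termination, against a Board decision). They can therefore call for different actions on identical data.

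Read as an instruction, the first sentence could also end the trial on very little evidence. Giant aneurysms are rare, so early counts such as one against none are to be expected by chance when treatment makes no difference. Stopping on such a count would leave the primary comparison (18% against 8%) unanswered. If the choice between paragraphs is left until cases appear, it will be made with those cases in view, in an open-label trial.

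**Working it through.** **1. The two paragraphs on the same counts (trial arm vs standard arm, equal denominators)**

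| Giant aneurysms | First paragraph | Second paragraph |
|---|---|---|
| 1 vs 0 | Terminate | No action |
| 4 vs 3 | Terminate | Report; Board decides |
| 4 vs 5 | Not met | Report; Board decides |

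The actions differ in every row.

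**2. Inputs**

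- Patients: "Target number of subjects: 196 per group, for a total of 392 patients" (section 12.2). A pooled normal-approximation formula without continuity correction gives 177 per arm for 18% vs 8%, against the stated 176. Then 176/0.9 = 195.6, so 196 per arm and 392 in total, as stated.
- Allocation 1:1 (section 6.2).
- Giant-aneurysm incidence 1.1% (upper figure) and 0.35% (survey), both from section 12.5. The 1.1% implies a high-risk share of 0.35/1.1 = 31.8%. The cohort in section 2.3.3 has (298 + 48)/1006 = 34.4% at high risk, which gives 0.35/0.344 = 1.02%, close to 1.1%.
- Assumption: the same true incidence in both arms.

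Expected cases at 1.1%: 392 × 0.011 = 4.3.

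**3. Comparison after every case**

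With equal incidence and 1:1 allocation, each case falls in the trial arm with probability 1/2. Given k cases in total,

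P(trial arm ahead at some point | k) = 1 − C(k, ⌊k/2⌋)/2^k.

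This is averaged over k ~ Binomial(392, 0.011):

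| k | P(k) | P(ahead at some point, given k) | Product |
|---|---|---|---|
| 0 | 0.013 | 0 | 0 |
| 1 | 0.057 | 0.500 | 0.029 |
| 2 | 0.124 | 0.500 | 0.062 |
| 3 | 0.179 | 0.625 | 0.112 |
| 4 | 0.194 | 0.625 | 0.121 |
| 5 | 0.168 | 0.688 | 0.115 |
| 6 | 0.120 | 0.688 | 0.083 |
| 7 | 0.074 | 0.727 | 0.054 |
| 8 | 0.040 | 0.727 | 0.029 |
| 9 or more | 0.031 | 0.754 or more | 0.024 |

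The sum is 0.628. The same calculation gives 0.609 with 176 per arm, 0.615 at 1.02% and 0.394 at 0.35%.

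**4. One comparison at the end**

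By symmetry, P(trial arm ahead) = (1 − P(tie))/2, with P(tie) the sum over j of the squared Binomial(196, q) probabilities.

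- q = 1.1%: (1 − 0.199)/2 = 0.400.
- q = 0.35%: (1 − 0.388)/2 = 0.306.

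**5. Periodic looks at 1.1% (simulation, at least one million runs)**

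| Looks | P(termination condition met) |
|---|---|
| Two (100 and 196 per arm) | 49% |
| Three, equally spaced | 53% |
| Six, equally spaced | 58% |

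Six looks correspond to twice-yearly monitoring (section 14.1) over a three-year registration period (section 12.2).

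**6. The four-case trigger, for comparison**

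P(X ≥ 4), X ~ Binomial(196, q): 17.1% at 1.1% and 0.5% at 0.35%. This leads to a review, not to termination.

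**The case against.** The best defence is that section 12.5 holds one rule with a loosely worded preamble. The first paragraph opens in general terms and gives the rationale. Only the second names a number, a reporting line and a decision-maker, and it is introduced by *Therefore*. The section heading speaks of an incidence that is high, which suits a count of four better than one against none. This is a plausible account of what was intended. It does not settle the matter: *Therefore* follows from the 1.1% figure, the mandatory sentence is never withdrawn or qualified, and the four-case trigger leaves out the control arm on which the first paragraph turns.

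A second objection stands. A reader might infer that a harmless treatment's trial would stop with 63% probability. That is the top of a range: it needs a by-arm comparison after every case, which the protocol does not schedule, and a rate that the protocol itself offers as an upper figure. Section 12.6 also restricts between-group comparisons on the primary and effectiveness endpoints before the end, apart from stated exceptions. A running comparison of a severe form of the primary outcome fits poorly with that, although giant aneurysm is not itself a listed endpoint.

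A third objection also stands. A reader might infer that four cases is a faulty threshold, because about 2.2 are expected at 1.1% (196 × 0.011) and the control arm is ignored. The documents do not support calling this an error. Four of 196 is 2.0%, nearly twice the upper figure, and the trigger only starts a review that the Board can close. The Board also receives regular monitoring reports with adverse events per group (sections 14.1 and 14.1.1). A between-arm trigger would be a trade-off, not a correction: with so few events, even 4 vs 0 in 196 per arm gives a two-sided Fisher p of about 0.12.

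**Conclusion.** The point holds as a conflict in the written text. Section 12.5 orders termination on any excess in the trial arm and then provides for a discretionary review at four cases, without saying which is operative.

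If the first sentence were applied literally to a treatment with no excess risk, the termination condition would be met with probability 40% to 63% at 1.1%, and about 31% to 39% at 0.35%, depending on how often the arms are compared. These figures assume equal true incidence, 196 patients per arm and 1:1 allocation, and they ignore efficacy stopping at the interim analysis (section 12.3.2). They describe what the sentence would do if followed. They do not forecast that the trial would stop, since the sponsor may well have meant the Board review to govern.

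No fault is found with the four-case threshold.

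**What to change.** Rewrite section 12.5 so that a single study-level provision is operative. State whether the Board-review sentence governs, and state that a bare numerical excess in the trial arm does not by itself end the study. The choice of rule belongs to the sponsor and the Board. Add that, when a review is triggered, the Board receives giant-aneurysm counts and numbers of patients for both arms.

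The cost is one reconciled paragraph, with a short note for the Board if wanted. No additional data and no change to the sample size are needed.

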12.6. Final Decision

When the follow-up period is completed and all the results of the final investigations have been determined, an analysis of all the study endpoints will be conducted. Until then, there will be no comparisons between groups with respect to either the primary endpoint or the secondary endpoints concerned with treatment effectiveness, unless such comparisons are added to the study protocol or special permission is received from the Efficacy and Safety Review Board.

The final results of all analyses will be assembled by the Data Coordinating Center into a Final Analysis Report, which will be submitted to the RAISE Study Office and the RAISE Study Principal Investigator. The RAISE Study Principal Investigator and the RAISE Study Office will then write a Summary Report for the use of clinical practitioners, based on the summarized contents of this Final Analysis Report, after careful consideration of the general conclusions of the study and an analysis and discussion of its problems and results, as well as suggestions for further research in this area. The study will then be considered finished.

13. ETHICAL CONSIDERATIONS

13.1. Patient protection

All researchers involved in the present study will strictly abide by the Helsinki Declaration in carrying out all the procedures of this study.

13.2. Informed consent

13.2.1. Explanation given to patients and their families

Before the patient is enrolled in the study, their attending physician will give the patient and/or the patient's family an explanatory document that has been approved by the IRB of that facility. If the patient is younger than 16 years, this document is to be handed to their guardian, and the following details are to be verbally explained:

- 1. The diagnosis of KD, its severity, and an explanation regarding its prognosis
- 2. The fact that they have the option of being enrolled in a clinical trial, with a detailed explanation of the difference between the meanings of "clinical trial" and "clinical practice"
- 3. The study design and its rationale (including its importance, the number of patients to be enrolled, its necessity, and its goals)
- 4. The content of the treatment protocol (the names and doses of the drugs to be administered, methods of administration, total duration of treatment and follow-up, and other important details, as requested)
- 5. The expected effect of the protocol treatment
- 6. Possible adverse events, complications, and sequelae, and clinical responses to these (known severity and incidence rates of various adverse events, as well as the clinical responses that will be undertaken in the event of their occurrence)
- 7. Responsibility for treatment costs and compensation (the physician will explain that the costs of the treatment will be covered by insurance, and that if permanent health problems arise from participating in the study, that compensation will be paid, the amount of which shall be equivalent to the compensation given for such events if they had arisen as a result of general medical practice)
- 8. The expected advantages and possible disadvantages to the patient arising from participation in the study
- 9. Access to patient medical history (an explanation of the external inspection of patient data, eg, "To ensure quality control, medical personnel from other facilities may receive permission from our hospital president to have direct visual access to patient medical records.")

- 10. Non-consent and withdrawal of consent (the fact that they are free to decline to participate in the study before the patient is enrolled and that, even after enrollment, they remain free at any time to withdraw from the study, and that such withdrawal will not in any way lessen the quality of care the patient receives)
- 11. Protection of human rights (the fact that all involved in the study will do their utmost to guarantee the confidentiality of the patient's identity and personal information)
- 12. The reuse of patient information (the possibility that the patient's data may be reused for scientific research, such as in meta-analyses, etc.), while maintaining patient anonymity
- 13. The right to ask questions (the patient and/or guardian(s) will be provided with a written document containing contact information for the attending physician, the facility chief investigator, and the RAISE Study Principal Investigator [and/or the RAISE Study Office]. The patient and/or guarantor(s) shall be informed that they are free to contact them and ask them any questions they might have, whether about the study or the treatment protocol).

13.2.2. Consent

After the patient and/or guarantor(s) have received the above explanations and have had a chance to confirm that they have indeed understood the contents of the study, they will be asked to participate in the study. If they consent to do so, the names of the physician who explained the above information and the patient and guarantor who consent to participate in the study will be written on the consent form appended to this protocol (or other suitable consent form as determined by the physician's institution), after which the physician and patient or guarantor will sign the document and add the date consent was given. Two copies will be made of this consent form, with one being given to the patient and/or guarantor(s), and one being retained by the facility coordinator. The original document will be kept in the file with the patient's medical records.

13.3. Protection of privacy and patient identification

The patient's full name will never be communicated to the Data Coordinating Center by the participating facility where s/he is receiving treatment. All references to patient identity will use the case number received at the time of patient registration and the patient's initials. The medical staff at the facility where the patient is being treated will know the patient's name, but there will be no record in the database at the Data Coordinating Center of personal information that could potentially be used by a third party to directly identify the patient.

13.4. Treatment in strict accordance with the study protocol

All investigators participating in the present study will strictly abide by all the rules detailed in this study protocol, except in cases where respecting these rules would require the investigators to endanger the patient or infringe upon the patient's human rights.

13.5. Approval by the Ethics Committee (Institutional Review Board) of each participating facility

13.5.1 Approval must be received before the facility can participate in the study

In order for a facility to participate in the study, this study protocol, together with the document that explains the treatment procedure to the patient and their family members, must be approved by that facility's Ethics Committee or Institutional Review Board (IRB). Once approval has been given by the facility's IRB, the facility coordinator shall fax a copy of the document showing their IRB approval to the Data Coordinating Center and keep the original document on file at their own facility.

14. MONITORING AND AUDITING

14.1. Regular monitoring

Regular monitoring will be carried out twice a year to guarantee the safety of the study subjects by ensuring study protocol adherence with regard to patient treatment and to confirm that all data are being correctly collected.

Central monitoring will be done with the aid of the information entered on the data sheets and collected at the Data Coordinating Center. If the Data Coordinating Center deems it necessary, onsite monitoring may also be done—by visiting respective facilities and comparing the original documents retained at these facilities with information stored in the Data Coordinating Center—together with other monitoring activities as required.

The Data Coordinating Center will produce regular Monitoring Reports and submit these reports to the RAISE Study Office, the RAISE Study Principal Investigator, and the Efficacy and Safety Review Board.

